1.2.1.3.1 Benefit-Risk Considerations in COVID-19

Plitidepsin has also been evaluated in a proof of concept (POC) study (APLICOV-PC) that included 46 hospitalised COVID-19 patients enrolled across 10 sites in Spain. As mentioned above, three doses of plitidepsin delivered as a 90-minute IV infusion were studied in this trial: 1.5, 2, and 2.5 mg, daily for 3 consecutive days (corresponding to 4.5, 6, and 7.5 mg per single course). Safety was the primary outcome of the POC study, which was assessed by the frequency of grade ≥ 3 AEs based on NCI CTCAE v.5.0 criteria, the percentage of patients with treatment-related and unrelated AEs, serious adverse events (SAEs), changes from baseline in haematologic and non-haematologic parameters, and percentages of patients with electrocardiogram (ECG) abnormalities (42).

AEs regardless of relationship are summarised by dose cohort and overall in Table 17 of the IB. Overall, 98% (44/45) of patients experienced at least one AE. The most common AEs by organ system, occurring in 2 or more ($\geq 4.4\%$) of patients overall were:

- Haematologic disorders: leukocytosis (6.7%), lymphopenia (6.7%)
- Gastrointestinal disorders: abdominal pain (8.9%), constipation (17.8%), diarrhoea (17.8%), dyspepsia (8.9%), nausea (42.2%), vomiting (17.8%)
- General disorders: asthenia (13.3%), pyrexia (44.4%)

- Infections: bacteremia (4.4%), COVID-19 pneumonia (6.7%), pneumonia (4.4%), urinary tract infection (4.4%)
- Investigations: ALT increased (11.1%), AST increased (6.7%), alkaline phosphatase increased (4.4%), C-reactive protein increased (24.4%), CPK increased (4.4%), ferritin increased (31.1%), fibrin D-dimer increased (17.8%), GGT increased (13.3%), LDH increased (8.9%), triglycerides increased (4.4%)
- Metabolic and nutrition disorders: decreased appetite (4.4%), hyperglycaemia (17.8%)
- Musculoskeletal disorders: back pain (4.4%)
- Nervous system disorders: dizziness (6.7%), dysgeusia (4.4%), headache (13.3%), insomnia (8.9%), presyncope (8.9%), somnolence (4.4%)
- Psychiatric disorders: delirium (4.4%)
- Renal: pre-renal failure (4.4%), renal impairment (4.4%)
- Respiratory: acute respiratory distress syndrome (8.9%), acute respiratory failure (4.4%), cough (24.4%), dyspnoea (15.6%), hypoxia (4.4%), tachypnea (4.4%)
- Vascular disorders: hypertension (4.4%), phlebitis (17.8%)

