No significant effects were observed on atrioventricular conduction or on depolarization in the protocol-specified analysis of ECGs, as no patient showed corrected QT interval by Fredericia [QTcF] >480 ms or change from baseline in QTcF >60 ms. Additionally, no significant effects were observed on atrioventricular conduction or on depolarisation, as measured by mean changes in PR and QRS intervals.

Liver test abnormalities: Although the majority of patients in the APLICOV-PC study experienced new or worsening abnormal liver function tests on study (with lab tests graded according to CTCAE v5.0), including increased ALT (65.9%), increased AST (29.5%), and increased GGT (38.6%), these events were reversible, mild, and short-lasting, as shown in Figure 10 of the IB for ALT, and no cases of hepatocellular injury were reported in the APLICOV-PC study. Notably, about one-third of patients had elevated liver function tests at baseline, including elevated ALT (grade 1 in 34.1% of patients), elevated AST (grade 1 in 36.4%), elevated GGT (grade 1 in 36.4%, grade 2 in 6.8% and grade 3 in 2.3%) and elevated LDH (grade 1 in 52.3%), but none had elevated bilirubin at baseline and no patients reported liver disease comorbidities at baseline. Although other studies of hospitalised COVID-19 patients have reported increased abnormal liver tests and increased liver injury with the use of the antiviral agents lopinavir, ritonavir and remdesivir (72, 73), there was no evidence of plitidepsin-induced liver injury in the APLICOV-PC study.

Nausea and vomiting: Nausea and vomiting were the most commonly reported AEs. A protocol amendment “AR9” was implemented in August 2020 to modify the prophylactic premedication given prior to plitidepsin infusion. Ondansetron 8 mg IV slow infusion was added and route of administration of dexamethasone was changed from oral to IV. The implementation of the aforementioned protocol amendment was associated with a reduction in the proportion of patients with nausea (from 55.5% to 38.9%) and vomiting (from 22.2% to 13.9%) and no new hypersensitivity reactions were seen in any of the 36 patients treated after the amendment (108 infusions) (See Table 18 of the IB).

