Laboratory Abnormalities: Laboratory abnormalities will be recorded and graded according to NCI-CTCAE version 5.0, accessible via internet (http://ctep.cancer.gov/protocolDevelopment/electronic_applications/docs/CTCAE_v5_Quick_Reference_8.5x11.pdf). Laboratory abnormalities that are of clinical significance will be recorded in Adverse Event eCRF.

Laboratory abnormalities for which NCI CTCAE grading is not available will be classified as the fold below the lower limit of normal (<LLN) or fold above the ULN.

All AEs will be graded according to the NCI-CTCAE v.5. Treatment modifications and reason for treatment discontinuation will be monitored throughout the study. The latest MedDRA dictionary version will be used for AE coding.

The safety profile of patients will be monitored throughout the treatment and at Day 60 (± 3 days), or until the date of death, whichever occurs first.

Any treatment-related AEs, treatment-emergent adverse events of special interest, and SAEs will be measured daily until resolution or stabilisation to at least Grade 1, or to an acceptable level according to the investigator and the Sponsor of his/her designated representative.

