7.4 ADVERSE EVENTS REPORTING PROCEDURES

7.4.1 Reporting of Adverse Events

The Sponsor will collect AEs from ICF signature until Day 60 (± 3 days) or until the date of death, whichever occurs first. All AEs suspected to be related to the study drug/IMP must be followed-up after the time of therapy discontinuation until the event or its sequelae resolve or stabilize at an acceptable level to the Investigator and the Sponsor.

All AEs, including medication errors and uses outside what is foreseen in the protocol, must be recorded in English using medical terminology in the source document and the e-CRF. Whenever possible, the Investigator will record the main diagnosis instead of the signs and symptoms normally included in the diagnoses.

Investigators must assess severity (grade) of the event following the NCI-CTCAE v.5 and assign a relationship to each study drug(s)/IMP(s); and pursue and obtain information adequate both to determine the outcome and to assess whether it meets the criteria for classification as a SAE requiring immediate notification to the Sponsor or its designated representative. The Investigator must provide any relevant information as requested by the Sponsor in addition to that already provided in the e-CRF.

Abnormal laboratory tests occurring during the study should only be recorded in the AE section of the e-CRF if the disorder:

- Is associated with clinically significant symptoms, and/or
- Leads to a discontinuation from the study, significant additional concomitant drug treatment or other therapy, and/or
- Leads to any of the outcomes included in the definition of a SAE.
- The test result is considered to be clinically relevant by the Investigator.

Otherwise laboratory results should be reported in the corresponding section of the e-CRF (e.g. biochemistry, haematology).

Signs and symptoms: all signs and symptoms present since the diagnosis of SARS-CoV-2 infection will be collected, including those related with the underlying disease or other concomitant conditions only if present at the time of ICF signature. A separate focus will be done on targeted COVID-19 signs and symptoms present within the last 24 h prior to screening and listed in [Appendix 10](#). They will be also monitored separately by the research team and collected in a specific form of the CRF.

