11.7.1 Adverse Event of Special Interest

The following AEs will be considered and monitored as AEs of special interest (AESIs): musculoskeletal disorders, CPK increases, and rhabdomyolysis; hypersensitivity reactions, cardiac events and transaminase elevations, thromboembolic events, and hepatobiliary disorders.

If at any time AST/ALT levels are greater than 3 x ULN (> 5 x ULN if pre-existent liver involvement at baseline by the underlying disease, with baseline ALT levels between 3-5 x ULN):

- Report as an AESI.
- The investigator should ensure that serum liver enzyme tests, serum bilirubin, and coagulation tests (INR or equivalent) are repeated two or three times weekly (local labs). Frequency of re-

testing can decrease to once a week or less if abnormalities stabilise or the trial drug has been discontinued and the subject is asymptomatic.

- The list of concomitant medications should be re-checked, and include nonprescription drugs, herbal and supplementary preparations, alcohol and recreational substances.
- Other reasons for liver injury should be ruled out, including co-infection with other virus, autoimmune or alcoholic hepatitis, non-alcoholic liver steato-hepatitis, biliary tract disease, progression of an underlying disease (e.g. liver metastasis), hypoxic/ischemic hepatopathy, or exposure to environmental agents.
- The investigator should consider additional tests to evaluate liver function or structure, as well as a consultation to specialists in liver diseases.

Treatment with plitidepsin must be discontinued in case of:

- ALT or AST > 8 x ULN;
- ALT or AST > 3 x ULN and either total bilirubin >2 x ULN or INR >1.5;
- ALT or AST > 3xULN with the appearance of fatigue, nausea, vomiting, right upper quadrant pain or tenderness, fever, rash, and/or eosinophilia (>5%).

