Adverse events of special interest (AESIs).	-Frequencies (severity grade by NCI-CTCAE v5)	-As treated population
Serious adverse events (SAEs).	-Frequencies (severity grade by NCI-CTCAE v5)	-As treated population
Drug related Serious Adverse Events (i.e., SARs).	-Frequencies (severity grade by NCI-CTCAE v5)	-As treated population
Adverse events leading to treatment discontinuation.	-Frequencies (severity grade by NCI-CTCAE v5)	-As treated population
Deaths (COVID-19-related/all).	-Frequencies	-As treated population
Change respect to baseline in individual study-defined laboratory parameters (See Protocol Section 5.7, 5.8 and 5.9 and Appendix 8 - Clinical Laboratory Analyses).	-Frequencies (severity grade by NCI-CTCAE v5)	-As treated population
Change respect to baseline in individual vital signs (See Protocol Section 5.7, 5.8 and 5.9).	-Frequencies	-As treated population
Other Secondary/Exploratory Endpoints		
Percentage of patients requiring advanced oxygen support on Days 4 (± 1), 8 (± 1), 15 (± 1), 30 (± 2), and 60 (± 3).	-Frequencies	-FAS population
Time to intensification of respiratory support (WHO >5) (See Protocol Appendix 1 – 11-Point World Health Organization (WHO) Clinical Progression Scale).	-Kaplan-Meier (unstratified)	-FAS population
Total duration of advanced oxygen support.	-Summary statistics	-FAS population

Endpoints	Analyses	Population
Percentage of patients requiring high-flow oxygen on Days 4 (± 1), 8 (± 1), 15 (± 1), 30 (± 2), and 60 (± 3).	-Frequencies	-FAS population
Total duration of high-flow oxygen therapy per patient.	-Summary statistics	-FAS population
Percentage of patients requiring non-invasive mechanical ventilation on Days 4 (± 1), 8 (± 1), 15 (± 1), 30 (± 2), and 60 (± 3).	-Frequencies	-FAS population
Total duration of non-invasive mechanical ventilation per patient.	-Summary statistics	-FAS population
Percentage of patients requiring invasive mechanical ventilation or ECMO on Days 4 (± 1), 8 (± 1), 15 (± 1), 30 (± 2), and 60 (± 3).	-Frequencies	-FAS population
Total duration of invasive mechanical ventilation or ECMO per patient.	-Summary statistics	-FAS population
Percentage of patients requiring admission to ICU on Days 4 (± 1), 8 (± 1), 15 (± 1), 30 (± 2), and 60 (± 3).	-Frequencies	-FAS population
Total duration of intensive care unit (ICU) stay.	-Summary statistics	-FAS population
Time to onset of additional (i.e., not present at baseline) immune-modulating drugs.	-Kaplan-Meier (unstratified)	-FAS population

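### Two reporting rules disagree on asymptomatic ALT/AST values above the AESI limit, so the transaminase AESI count could miss some and depends on how each site read the rules

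*SAP*

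**What the plan says.** Protocol 7.2.1 and SAP 11.7.1 list transaminase elevations and CPK increases among the AESIs. For transaminases they add a numeric trigger. It begins "If at any time AST/ALT levels are greater than 3 x ULN" and carries an exception, "> 5 x ULN if pre-existent liver involvement at baseline by the underlying disease, with baseline ALT levels between 3-5 x ULN". A value past the limit is to be reported as an AESI. CPK has no numeric trigger.

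Protocol 7.4.1 sets a general filter for laboratory results: "Abnormal laboratory tests occurring during the study should only be recorded in the AE section of the e-CRF if the disorder" meets one of four criteria. These are clinically significant symptoms, discontinuation or significant added treatment, a serious-event outcome, or the last one, "The test result is considered to be clinically relevant by the Investigator". Other results go to the laboratory section of the e-CRF. Protocol 7.2 has a shorter version, "Laboratory abnormalities that are of clinical significance will be recorded in Adverse Event eCRF", and Protocol 7.3.1 uses similar criteria.

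SAP 11.7 takes treatment-emergent events from the investigators' verbatim e-CRF terms. Table 3 in SAP 11.8 reports AESIs as frequencies by CTCAE grade in the As Treated population. Separately, SAP 11.7 plans worst laboratory grade and shift tables, and its panel includes ALT, AST and CPK.

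**The concern.** One rule is triggered by a number, the other by clinical consequence or opinion. A patient with an ALT of 4 x ULN, no symptoms, no treatment change and no judgement of relevance is an AESI under the first and stays off the AE form under the second. Nothing exempts AESIs from the filter, and the SAP has no step that derives an AESI from the laboratory data.

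Investigators know the arm, so a relevance judgement can differ between arms for the same value. SAP 6.0 limits the report to safety and descriptive efficacy and expects readers to compare the arms numerically from descriptive tables. The AESI frequencies are among those tables. Part of any difference in them could come from recording practice, although ALT and AST are measured at scheduled central-laboratory visits in both arms.

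**Working it through.** No design figure is involved, so there is none of the plan's own to reproduce. The check is a comparison of rules, followed by a look at what the documents say about size.

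**1. The two rules applied to one value** (eligible patient, baseline ALT not above 3 x ULN, post-baseline ALT 4 x ULN)

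- Protocol 7.2.1 / SAP 11.7.1: 4 > 3, and the liver exception does not apply, so it is reported as an AESI.
- Protocol 7.4.1: with no symptoms, no discontinuation or added treatment and no serious outcome, it reaches the AE form only if the investigator calls it relevant.
- SAP 11.7 and Table 3: AESIs are defined as adverse events, and treatment-emergent events come from investigator terms. The value is counted if the site followed the first rule. It can be missing if the site followed the second and did not judge it relevant.

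**2. CPK.** No limit is stated, so no two rules conflict. The count rests on judgement because a cut-off is absent.

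**3. What the documents offer on size.** Protocol 1.2.1.3.1 gives both kinds of rate for APLICOV-PC. The adverse-event denominator of 45 is stated. The laboratory denominator of 44 is inferred: it is the only value from 43 to 46 that gives the printed percentages.

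- ALT: adverse events 5/45 = 11.1%; laboratory 29/44 = 65.9%; ratio 11.1/65.9 = 0.17.
- AST: adverse events 3/45 = 6.7%; laboratory 13/44 = 29.5%; ratio 6.7/29.5 = 0.23.

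AE forms and laboratory data can therefore differ widely for changes in general. The ratios do not measure loss above the AESI limit. The laboratory changes were of any grade and are described as mild, that study's recording rules are not given, and reading the ratio as a capture rate assumes that every patient with the adverse event also had the laboratory change.

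**4. Illustration on assumed values.** Take the planned 60 per arm (3 groups x 20) and the same true rate above the limit in both arms. Suppose one arm records all cases and the other half.

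- True 5%: 60 x 0.05 = 3 against 1.5 expected cases, shown as 5% against 2.5%.
- True 10%: 6 against 3, shown as 10% against 5%.
- True 20%: 12 against 6, shown as 20% against 10%.

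If both arms record half, both rates halve and the arms stay equal. The recording shares and true rates are assumptions, either arm could be the one under-recorded, and actual enrolment was below plan.

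**The case against.** The strongest reply is that a specific mandatory instruction normally overrides a general one. A value above the limit also sets off repeat liver tests two or three times weekly, a medication check and a search for other causes. Most investigators would call such a value clinically relevant, and it would then pass the filter. The CRF is not among the documents and may carry an AESI prompt. SAP 3.0 has no formal significance tests, and no decision rule in it uses the AESI rate.

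Much of this stands. It makes large losses less likely and limits the consequence. It does not remove the ambiguity: neither document states precedence, and the count still depends on each site having settled the question the same way.

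A reader might also infer several stronger things that the documents do not support:

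- **Every ALT/AST above 3 x ULN is an AESI.** The same sentence raises the limit to 5 x ULN for one subgroup.
- **AE forms miss about five in six ALT rises of the kind at issue.** The APLICOV-PC figures concern mild changes of any grade.
- **Liver or muscle toxicity is hidden, or the laboratory data go unused.** The worst-grade and shift tables use those data directly.
- **The rules conflict for CPK.** Only a cut-off is missing.
- **The bias favours one arm.** Nothing shows a direction.

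**Conclusion.** The point holds in a limited form. For transaminases, the AESI trigger and the laboratory filter can give opposite answers for the same asymptomatic value, and no text resolves them. The AESI frequencies in Table 3 could therefore understate the number of patients above the plan's own limit, and they depend partly on open-label judgement and site reading. The size and direction of any loss cannot be obtained from the documents.

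This affects the AESI rows and not the laboratory tables. None of those tables is specified as a count of patients above the AESI limit, and no step reconciles them with the AESI table, so a reader could meet two different liver pictures without explanation. The conclusion assumes that AESIs reach the analysis through the AE form, as SAP 11.7 implies. A separate AESI form or flag in the CRF would weaken it. It is a cheap improvement to a descriptive table and does not threaten the trial's main results. Whether the limits themselves are clinically right is not judged here.

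**What to change.** In SAP 11.7.1 and Table 3, for the As Treated population and by arm:

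- Add a laboratory-derived transaminase row: patients with any post-baseline ALT or AST above the plan's existing AESI limit, liver exception included. Count unscheduled values too, since the trigger applies at any time.
- Add a second count restricted to scheduled central-laboratory visits, so that the arms are compared on equal sampling. The first count alone could be affected by extra local testing in one arm.
- Show investigator-reported AESIs in separate rows.
- For CPK, place the already planned worst laboratory CTCAE grade beside the investigator-reported AESI. Do not define a new AESI threshold.

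Protocol 7.2.1 / SAP 11.7.1 and Protocol 7.4.1 must be reconciled. Recruitment has ended, so a protocol edit cannot change reports already made, and the SAP change is the effective repair. Because the data were unmasked on 19 March 2024, the new rows should be labelled as added after unmasking. They use a limit already in the plan, so no threshold is chosen from the data.

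The cost is a little programming on data already collected. Stated AESI rates may rise in both arms, and the report will need a sentence explaining why the laboratory-derived and reported counts differ.

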11.7.2 IDMC safety report

IDMC requested specific outputs based on the publication (submitted): DMC reports in the 21st century. Towards better tools for decision-making, Vandemeulebroecke M., Baillie, M. Mirshani, A. and Lesaffre E.

Due to the premature study closure and suspension of the IDMC activity, no specific outputs or sensitivity analyses will be generated

11.8 Summary of Statistical Tests

All the main characteristics for estimands to fulfill study objectives will be defined as footnotes in each table following a similar structure than primary estimand definition. Below it can be found the endpoints to measure the variable definition and the analysis method to be used. Treatment attribute is maintained as 'participants will be randomised to receive plitidepsin versus control in each group' whereas applicable and sensitivity analyses according populations defined in 8.5 will be calculated. For intercurrent events, while applicable, a treatment-policy strategy as defined for the primary estimand will be followed.

Table 3 Summary of statistical tests

Endpoints	Analyses	Population
Efficacy primary endpoint		
1-month all-cause mortality rate.	-Frequencies	-FAS population
Key secondary endpoint		
Time to confirmed negativisation in SARS-CoV-2 antigen test or RT-PCR Ct > 30.	-Kaplan-Meier (unstratified)	-FAS population

Endpoints	Analyses	Population
Efficacy secondary endpoints		
Time to sustained end of COVID-related hospital care from the time of randomisation. Sustained discharge is defined as no subsequent admission within 30 days of initial end of hospital care [up to day 60 (± 3)], related to either COVID-19 or COVID-19 therapy	-Kaplan-Meier (unstratified)	-FAS population
Time to sustained improvement (defined in Protocol Section 7.1.3) and resolution of selected COVID signs/symptoms (See Protocol Appendix 10 - COVID-19 signs/symptoms checklist).	-Kaplan-Meier (unstratified)	-FAS population
Distribution of patients according to their clinical status by the 11-category WHO Clinical Progression Scale, at Days 4 (± 1), 8 (± 1), 15 (± 1), 30 (± 2), and 60 (± 3) (See Protocol Appendix 1 – 11-Point World Health Organization (WHO) Clinical Progression Scale).	-Frequencies	-FAS population
Percentage of patients requiring oxygen therapy on Days 4 (± 1), 8 (± 1), 15 (± 1), 30 (± 2), and 60 (± 3).	-Frequencies	-FAS population
Time to sustained discontinuation (i.e., at least 7 days) of oxygen supplementation.	-Kaplan-Meier (unstratified)	-FAS population
Safety secondary endpoints		
Treatment-emergent adverse events (TEAEs).	-Frequencies (severity grade by NCI-CTCAE v5)	-As treated population
TEAEs \geq grade 3 according to the National Cancer Institute	-Frequencies	-As treated population

Endpoints	Analyses	Population
[NCI]-Common Terminology Criteria for AEs (CTCAE v.5.0).		
Adverse events of special interest (AESIs).	-Frequencies (severity grade by NCI-CTCAE v5)	-As treated population
Serious adverse events (SAEs).	-Frequencies (severity grade by NCI-CTCAE v5)	-As treated population
Drug related Serious Adverse Events (i.e., SARs).	-Frequencies (severity grade by NCI-CTCAE v5)	-As treated population
Adverse events leading to treatment discontinuation.	-Frequencies (severity grade by NCI-CTCAE v5)	-As treated population
Deaths (COVID-19-related/all).	-Frequencies	-As treated population
Change respect to baseline in individual study-defined laboratory parameters (See Protocol Section 5.7, 5.8 and 5.9 and Appendix 8 - Clinical Laboratory Analyses).	-Frequencies (severity grade by NCI-CTCAE v5)	-As treated population
Change respect to baseline in individual vital signs (See Protocol Section 5.7, 5.8 and 5.9).	-Frequencies	-As treated population
Other Secondary/Exploratory Endpoints		
Percentage of patients requiring advanced oxygen support on Days 4 (± 1), 8 (± 1), 15 (± 1), 30 (± 2), and 60 (± 3).	-Frequencies	-FAS population
Time to intensification of respiratory support (WHO >5) (See Protocol Appendix 1 – 11-Point World Health Organization (WHO) Clinical Progression Scale).	-Kaplan-Meier (unstratified)	-FAS population
Total duration of advanced oxygen support.	-Summary statistics	-FAS population

Endpoints	Analyses	Population
Percentage of patients requiring high-flow oxygen on Days 4 (± 1), 8 (± 1), 15 (± 1), 30 (± 2), and 60 (± 3).	-Frequencies	-FAS population
Total duration of high-flow oxygen therapy per patient.	-Summary statistics	-FAS population
Percentage of patients requiring non-invasive mechanical ventilation on Days 4 (± 1), 8 (± 1), 15 (± 1), 30 (± 2), and 60 (± 3).	-Frequencies	-FAS population
Total duration of non-invasive mechanical ventilation per patient.	-Summary statistics	-FAS population
Percentage of patients requiring invasive mechanical ventilation or ECMO on Days 4 (± 1), 8 (± 1), 15 (± 1), 30 (± 2), and 60 (± 3).	-Frequencies	-FAS population
Total duration of invasive mechanical ventilation or ECMO per patient.	-Summary statistics	-FAS population
Percentage of patients requiring admission to ICU on Days 4 (± 1), 8 (± 1), 15 (± 1), 30 (± 2), and 60 (± 3).	-Frequencies	-FAS population
Total duration of intensive care unit (ICU) stay.	-Summary statistics	-FAS population
Time to onset of additional (i.e., not present at baseline) immune-modulating drugs.	-Kaplan-Meier (unstratified)	-FAS population
Percentage of patients receiving immune-modulating drugs on Days 1, 4 (± 1), 8 (± 1), 15 (± 1), 30 (± 2), and 60 (± 3).	-Frequencies	-FAS population
Time to onset of additional (i.e., not present at baseline) antiviral drugs.	-Kaplan-Meier (unstratified)	-FAS population

Endpoints	Analyses	Population
Percentage of patients receiving subsequent antiviral drugs (i.e., not present at baseline) on Days 4 (± 1), 8 (± 1), 15 (± 1), 30 (± 2), and 60 (± 3).	-Frequencies	-FAS population
Percentage of patients with a new infection by Days 4 (± 1), 8 (± 1), 15 (± 1), 30 (± 2), and 60 (± 3).	-Frequencies	-FAS population
Cumulative mortality (all-cause and related to COVID-19) by Days 4 (± 1), 8 (± 1), 15 (± 1), 30 (± 2), and 60 (± 3).	-Frequencies	-FAS population
Percentage of patients in each study group who require subsequent admission within 30 days of initial end of hospital care [up to day 60(± 3)], related to either COVID-19 or COVID-19 therapy.	-Frequencies	-FAS population
Change respect to Day 1 in the viral load of SARS-CoV-2, measured by RT-PCR, by Days 4 (± 1), 8 (± 1), 15 (± 1), 30 (± 2), and 60 (± 3), in each study group.	-Summary statistics	-FAS population
Percentage of patients in each study group with undetectable viral load, by Days 4 (± 1), 8 (± 1), 15 (± 1), 30 (± 2), and 60 (± 3).	-Frequencies	-FAS population
Time to either undetectable viral load of SARS-CoV-2 or > 2 logs reduction respect to Day 1.	-Kaplan-Meier (unstratified)	-FAS population
Change respect to baseline in inflammatory biomarkers (C-reactive protein [CRP], procalcitonin, lactate dehydrogenase [LDH], ferritin, neutrophil-to-lymphocyte ratio, and multiplex cytokines assay,	-Summary statistics	-FAS population

Endpoints	Analyses	Population
by Day 4 (± 1), 8 (± 1), 15 (± 1) and 30 (± 2) and 60 (± 3).		
Change respect to baseline in individual serological assessments against SARS-CoV-2, by Days 30 (± 2), and 60 (± 3).	-Summary statistics	-FAS population
Change respect to baseline in individual T-cell response against SARS-CoV-2 by Days 30 (± 2), and 60 (± 3).	-Summary statistics	-FAS population
Change respect to baseline to Days 15 (± 1), and 30 (± 2) in chest X-ray findings (Brixia score, centrally assessed) (Protocol Appendix 9 – Brixia Score).	-Summary statistics	-FAS population
Percentage of patients requiring modification of the therapy (drugs, dose or schedule) for the underlying disease.	-Frequencies	-FAS population
Time in which pre-scheduled therapies for the control of the underlying disease were not able to be administered.	-Kaplan-Meier (unstratified)	-FAS population
Risk for mortality / clinical deterioration according to individual clinical characteristics and laboratory observations present at baseline, scores of validated scales (e.g., ISARIC-4C), as well as features related to COVID-19 [including SARS-CoV-2 variant (if available), vaccination status, duration of the infection, and inflammation-related parameters [neutrophil-to-lymphocyte ratio (NLR), protein C reactive, interleukine-6 (IL-6) and lymphocytes], the underlying disease, and other co-morbidities.	-Frequencies	-FAS population

Endpoints	Analyses	Population
-----------	----------	------------

<NOTE: Due to the premature study closure no Bayesian or specific outputs or sensitivity analyses will be generated>.

11.9 Vital signs, Physical Examinations, ECGs, Chest Imaging and Other Observations Related to Safety

Vital signs, physical examination, ECGs, chest imaging and respiratory assessments data including oxygen therapy supplementation status and their changes from baseline will be summarized by visit using standard descriptive statistics for the as treated population.

